3.1.1 Definition of Dose Limiting Toxicity

The National Cancer Institute Common Toxicity Criteria for Adverse Events (NCI CTCAE) version 4.03 will be used throughout this study. The definition of DLT for the purpose of dose escalation decisions includes any of the following events considered to be causally related to treatment with an investigational study treatment in combination with nivolumab that occurs during the first 28-day treatment cycle:

• Any Grade 4 non-hematological toxicity.

- Any Grade 3 non-hematological toxicity or Grade 3 or 4 hematological toxicity that does not recover to ≤ Grade 2 as indicated by symptoms within 3 days and/or as indicated by laboratory assessment within 8 days after onset of the event despite optimal medical management with or without corticosteroids.
 - A special case is provided for hepatic transaminases increase over baseline by two-fold or more and meeting Grade 3 or 4 criteria.
- Grade 2 pneumonitis or colitis that does not resolve to ≤ Grade 1 as indicated by symptoms within 3 days after onset of the event despite optimal medical management with or without corticosteroids.
- Febrile neutropenia or neutropenia associated with systemic infection.
- Any toxicity that requires suspension of treatment for more than 2 weeks.

The definition of DLT excludes the following conditions:

- Grade 3 fatigue lasting \leq 7 days.
- Grade 3 endocrine disorder (thyroid, pituitary, and/or adrenal insufficiency) that can be effectively managed with hormone replacement therapy.
- Acute infusion-related reaction.
- Lymphopenia without infection.
- Thrombocytopenia without clinically significant bleeding.

3.1.2 Enrollment and Dose Escalation Plan

Patients meeting eligibility criteria as outlined in this protocol may enroll into the lead-in dose escalation evaluation, regardless of whether they did or did not experience clinical benefit during prior treatment with a checkpoint inhibitor. Dose escalation cohorts are expected to include between 3 and 8 patients for each investigational study treatment and dose level evaluated. The first patient to be treated at the starting dose and at each new higher dose of investigational study treatment will be observed for at least one week prior to enrollment of subsequent patients in the cohort. As many as 5 patients may initially be enrolled into each cohort. For a patient within a dose cohort to be considered evaluable for the dose-escalation decision, the patient must have either been on study for one full cycle and have received treatment with nivolumab and at least 75% of scheduled investigational study treatment doses in Cycle 1 or have experienced a DLT in Cycle 1. Decision making for cohort expansion and dose escalation or de-escalation will be in accordance with the mTPI method (Dose-Finding Spreadsheet presented in Appendix 2). To ensure sufficient patient experience at the dose to be used in the Phase 2 study, enrollment at any dose level under consideration may be expanded to include at least 6 patients.

3.1.3 Definition of Maximum Tolerated Dose

The Maximum Tolerated Dose (MTD) is defined as the highest investigational study treatment dose administered in the combination regimen associated with the decision to "stay with the current dose" as determined from the Dose-Finding Spreadsheet (Appendix 2) using the experience of at least 6 patients during the first 28-day treatment cycle.

3.1.4 Selection of Phase 2 Dose for Investigational Study Drugs

For each investigational study drug, the dose to be selected for use in the Phase 2 study will be the highest dose evaluated in the lead-in evaluation that is associated with:

- sufficient safety/tolerability to anticipate that patients will typically be able to receive treatment with at least 75% of the intended dose intensity of investigational study treatment and 100% dose intensity of nivolumab; and
- no observed \geq Grade 3 or serious irAEs causally related to the combination regimen.

A dose level below the MTD may be selected for use in the Phase 2 study.

3.2 Phase 2 Study

Following completion of the lead-in dose escalation evaluation, enrollment into the Phase 2 study will proceed.

The treatment arms included in this study are the following:

- 1. Glesatinib plus nivolumab.
- 2. Sitravatinib plus nivolumab.
- 3. Mocetinostat plus nivolumab.

For patients who have experienced progression of disease on or after treatment with a checkpoint inhibitor (CIT-experienced), enrollment into each treatment arm will be stratified by prior outcome of treatment with a checkpoint inhibitor:

- a. Clinical benefit (i.e., RECIST defined partial or complete response or stable disease for at least 12 weeks [-2 week window permitted for radiograph scheduling]) followed by radiographic progression of disease.
- b. No prior clinical benefit (i.e., radiographic progression of disease ≤ 12 weeks after initiation of treatment [+2 week window permitted for radiograph scheduling]).

Thus, the study will include 6 parallel evaluations of clinical activity of nivolumab combination regimens (Figure 3) in patients with prior treatment with a checkpoint

inhibitor. Patients enrolled in the lead-in dose escalation evaluation and receiving the dose of investigational study treatment chosen for the Phase 2 study will be included in the analysis of the Phase 2 endpoints. Patients who discontinue the study prior to the first on-study disease assessment for reasons other than disease progression may be replaced.

For patients without prior checkpoint inhibitor therapy (CIT-naïve), each investigational study treatment arm (i.e., glesatinib, sitravatinib, and mocetinostat) will be stratified according to PD-L1 status:

- a. Having tumor with no/low PD-L1 expression.
- b. Having tumor with high PD-L1 expression.

Tumor PD-L1 expression will be determined by the PD-L1 (28-8) companion diagnostics assay completed through the central laboratory. No/low PD-L1 expression is defined as positivity < 5% of tumor cells; high PD-L1 expression is defined as positivity $\ge 5\%$ of tumor cells. Tumor samples used to establish PD-L1 expression for eligibility must have been collected after the most recent systemic therapy.

Thus, the study will include 6 parallel evaluations of clinical activity of nivolumab combination regimens (Figure 3) in patients without prior treatment with a checkpoint inhibitor.

Disease response and progression as documented by the Investigator in the Case Report Form (CRF) will be the basis for patient management and study expansion decision making. Unconfirmed objective responses recorded in the CRF may be used as the initial basis for expansion of study enrollment; however, follow-up evaluations on patients with unconfirmed responses must continue to support the decision to continue to the full number of patients to be included in the next stage. Disease assessments will be performed until objective disease progression is documented or subsequent anti-cancer therapy is begun. Central radiology review for disease response and progression may be added to the study during Stage 2. If this occurs, central review of all radiologic assessments performed in the study will be expected (including retrospective review of patients enrolled in Stage 1), and central radiology review for disease response will be the basis for the primary statistical analyses to estimate the objective response rate and its confidence interval, as well as the duration of response and PFS.

Statistical Design Applied to CIT-Experienced and CIT-Naïve with No/Low PD-L1 Expression

This Phase 2 study will use a Predictive Probability Design (Lee-2008) in each treatment arm and strata. In creating the statistical designs, the Type 1 error (α) is constrained to <0.05 and Power (1- β) is constrained to \geq 0.90.

The ORR using nivolumab in the population with advanced non-squamous NSCLC having prior disease progression on a checkpoint inhibitor or patients with non-squamous NSCLC without prior checkpoint inhibitor therapy with no/low PD-L1 expression is

assumed to be 5% (p₀); thus this rate is considered uninteresting. The target ORR using the investigational agents in combination with nivolumab in this study is 30% (p₁). Stage 1 of enrollment will include a minimum of 9 evaluable patients in each treatment strata. With exactly 9 evaluable patients at Stage 1, if at least 1 patient has an Objective Response, 8 additional evaluable patients will be enrolled in the treatment stratum, for a total sample size of 17 evaluable patients. If at least 3 Objective Responses are observed in a treatment stratum, further investigation may be warranted. If the true ORR is 5% (null hypothesis), the probability of early termination during the study is 0.63; the Type 1 error is equal to 0.0466 and the power is equal to 0.9045.

Statistical Design Applied to CIT-Naïve with High PD-L1 Expression

The ORR using nivolumab in the population with non-squamous NSCLC having high PD-L1 expression is assumed to be 27% (p_0); thus this rate is considered uninteresting. The target ORR using the investigational agents in combination with nivolumab is 50% (p_1).

Stage 1 of enrollment will include approximately 17 evaluable patients. With exactly 17 evaluable patients at Stage 1, if at least 5 patients have Objective Responses, 27 additional evaluable patients will be enrolled, for a total sample size of 44 evaluable patients. If at least 18 Objective Responses are observed, further investigation may be warranted. If the true ORR is 27% (null hypothesis), the probability of early termination during the study is 0.50; the Type 1 error is equal to 0.0303 and the power is equal to 0.9018.

The exact stopping rules for all cohorts will be calculated based on the Predictive Probability Design, once the exact number of patients evaluable at Stage 1 is known. The aim is to get a minimum of 9 evaluable patients at Stage 1 for CIT-experienced and CIT-naïve with no/low PD-L1 expression cohorts and a minimum of 17 evaluable patients at Stage 1 for CIT-naïve with high PD-L1 expression cohort.

In order to be part of the clinical activity evaluable population, the patient must have at least one on-study disease assessment or discontinue from treatment for progressive disease prior to this assessment. Patients who discontinue treatment prior to the first on-study disease assessment for an AE, toxicity, or withdraw consent are considered non-evaluable for disease assessment. These patients will not be part of the clinical activity evaluable population.

[figure not shown]
Expansion Beyond Stage 2

[figure not shown]
The original protocol provided that if results in any strata were of high interest for efficacy, enrollment might be expanded to as many as 100 patients total in each cohort to narrow the 95% Confidence Interval (CI) around the ORR point estimate. Protocol Amendment 3 (Version 4.0) eliminates enrollment expansion beyond Stage 2 except in the sitravatinib segment of the study enrolling patients with CIT-experience.

For the sitravatinib segment of the study enrolling patients with CIT-experience, expansion of enrollment beyond Stage 2 will be managed as one cohort that includes all patients, regardless of prior clinical benefit during treatment with CIT. Based on preliminary clinical activity results as of June 2018 (described in Section 1.5.3.2.2), enrollment into the combined cohort will expand to as many as 125 patients total, to further evaluate safety and efficacy in this setting.

Expansion of sitravatinib CIT-naïve cohorts beyond Stage 2 of enrollment is not anticipated.

Figure 3: Study Diagram

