a. Clinical benefit (i.e., RECIST defined partial, complete response or stable disease for at least 12 weeks [-2 week window permitted for radiograph scheduling]) followed by radiographic progression of disease.

[figure not shown]
b. No prior clinical benefit (i.e., radiographic progression of disease ≤ 12 weeks after initiation of treatment [+2 week window permitted for radiograph scheduling]).

[figure not shown]
For patients without prior checkpoint inhibitor therapy (CIT-naïve), each investigational study treatment arm (i.e., glesatinib, sitravatinib, and mocetinostat) will be stratified according to PD-L1 status:

- a. Having tumor with no/low PD-L1 expression.
- b. Having tumor with high PD-L1 expression.

Tumor PD-L1 expression will be determined by the PD-L1 (28-8) companion diagnostics (CDx) assay completed through the central laboratory. No/low PD-L1 expression is defined as positivity < 5% of tumor cells; high PD-L1 expression is defined as positivity $\ge 5\%$ of tumor cells. Tumor samples used to establish PD-L1 expression for eligibility must have been collected after the most recent systemic therapy.

The main Phase 2 study will include 12 parallel evaluations of clinical activity of nivolumab combination regimens (depicted in the figure below). A Predictive Probability Design will be applied to each treatment arm, as described under Statistical Considerations. Patients enrolled in the lead-in dose escalation evaluation and receiving the dose of investigational study treatment selected for the Phase 2 study will be included in the analysis of the Phase 2 endpoints.

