4.1 Inclusion Criteria

Patients must meet all of the following inclusion criteria as applicable for phase of the study to be eligible for enrollment into the study:

- 1. Histologically confirmed non-squamous NSCLC with metastatic or unresectable, locally advanced disease, not amenable to treatment with curative intent.
- 2. Receipt of at least one prior treatment in the advanced disease setting.
 - a) CIT-experienced: Most recent treatment must have included a checkpoint inhibitor (i.e., anti-PD-1 or anti-PD-L1 including nivolumab, pembrolizumab, durvalumab, atezolizumab or avelumab) with the result of progression of disease on or after treatment.

Note: For the PK sub-studies as outlined within Appendix 5 and Appendix 6, treatment with a checkpoint inhibitor (i.e., anti-PD-1 or anti-PD-L1) does not need to be included in the most recent treatment.

- b) CIT-naïve: Receipt of prior platinum-based doublet chemotherapy.
- 3. CIT-naïve: Molecular analysis of tumor sample collected following most recent therapy, assessed using the PD-L1 (28-8) CDx assay. Inclusion in the treatment arm will be based on documented no/low PD-L1 expression (positivity < 5% of tumor cells) or high PD-L1 expression (positivity ≥ 5% of tumor cells). *Note: This criterion does not apply to the PK sub-studies as outlined within Appendix 5 and Appendix 6.*
- 4. Measurable disease as per RECIST version 1.1.
- 5. Eastern Cooperative Oncology Group (ECOG) performance status 0, 1 or 2 (Appendix 1).
- 6. Adequate bone marrow and organ function demonstrated by:
 - Absolute neutrophil count $\geq 1,000/\text{mm}^3 \ (\geq 1.0 \times 10^9/\text{L})$
 - Platelet count $\ge 50 \times 10^9 / L \ (> 50,000 \text{ per mm}^3)$

- Alanine aminotransferase (ALT) and aspartate aminotransferase (AST)
 ≤ 2.5 × Upper Limit of Normal (ULN), or ≤ 5.0 × ULN for patients with documented liver metastases.
- Serum bilirubin $\leq 1.5 \times \text{ULN}$ or $\leq 3.0 \times \text{ULN}$ for patients with Gilbert Syndrome or documented liver metastases.
- Serum creatinine $\leq 1.5 \times ULN$.
- 7. \geq 18 years of age.
- 8. Women of child-bearing potential (WOCBP) or men whose partner is a WOCBP agrees to use contraception while participating in this study, and for a period of 6 months following termination of study treatment.
- 9. Completed informed consent process, including signing IRB/EC-approved informed consent form.
- 10. Willing to comply with clinical trial instructions and requirements.

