Potential exists for individual tumor lesions to develop necrosis, to cavitate, have a flare response to treatment or become otherwise difficult to evaluate for a period of time as the result of beneficial study treatment impact. For example, tumor necrosis, cavitation or flare may result in increase in overall size of individual lesions or unclear tumor margins prior to recovery to smaller lesions, development of scar tissue, or complete resolution. The true tumor measurements of lesions should be recorded but the conclusion of progressive disease may be suspended until continued assessment clarifies the nature of the tumor change. If repeat assessments indicate progression of disease, then PD should be recorded on the date of the first assessment giving the impression of progression. If repeat assessments indicate that the change was a process of transition, then NE (not evaluable) should be recorded during the period of transition, and PR or CR may be recorded for subsequent evaluations. The CRF will collect information on the observations during the period of transition to support the assessment conclusions.

Supplemental Investigations

If CR determination depends on a residual lesion that decreased in size but did not disappear completely, it is recommended the residual lesion be investigated with biopsy or fine needle aspirate. If no disease is identified, objective status is CR.

Best Objective Response

Target Lesions	Non-Target Lesions	New Lesion	Point in Time Response	Best Response
CR	CR	No	CR	CR and PR require
CR	Non-CR/Non-PD	No	PR	confirmation at least 4 weeks after first
PR	Non-PD	No	PR	observation
SD	Non-PD	No	SD	SD requires an on-study assessment after at least 6weeks on treatment. Unconfirmed PR or CR are reported as SD.
PD	Any	Yes or No	PD	
Any	PD	Yes or No	PD	
Any	Any	Yes	PD	

Patientive Progression

Patients requiring discontinuation of treatment due to worsening health status attributable to advancement of the malignancy under study but without objective evidence of disease progression should not be reported as PD on tumor assessment CRFs. This should be indicated on the end of treatment CRF as off treatment due to Global Deterioration of Health Status.

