6.2 Phase 2 Study

Following completion of the lead-in phase dose escalation evaluation, enrollment into the Phase 2 study will proceed. The treatment arms included in this study are the following:

1. Glesatinib plus Nivolumab
2. Sitravatinib plus Nivolumab
3. Mocetinostat plus Nivolumab

For patients who have experienced progression of disease on or after treatment with a checkpoint inhibitor (CIT-experienced) enrollment into each treatment arm will be stratified by prior outcome of treatment with a checkpoint inhibitor:

- a. Clinical benefit (i.e., RECIST defined CR, PR or SD for at least 12 weeks [-2 week window permitted for radiograph scheduling]) followed by radiographic progression of disease.
- b. No prior clinical benefit (i.e., radiographic progression of disease \leq 12 weeks after initiation of treatment [+2 week window permitted for radiograph scheduling]).

Thus, the study will include 6 parallel evaluations of clinical activity of Nivolumab combination regimens (Figure 1) in patients with prior treatment with a checkpoint inhibitor. Patients enrolled in the lead-in phase dose escalation evaluation and receiving the dose of investigational study drug chosen for the Phase 2 study will be included in the analysis of the Phase 2 endpoints. Patients who discontinue the study prior to the first on-study disease assessment for reasons other than disease progression may be replaced.

For patients without prior CIT (CIT-naïve), each investigational study treatment arm (i.e., Glesatinib and Sitravatinib) will be stratified according to PD-L1 status:

- a. Having tumor with no/low PD-L1 expression.
- b. Having tumor with high PD-L1 expression.

Tumor PD-L1 expression will be determined by the PD-L1 (28-8) companion diagnostics assay completed through the central laboratory. No/low PD-L1 expression is defined as positivity $< 5\%$ of tumor cells; high PD-L1 expression is defined as positivity $\geq 5\%$ of tumor cells. Tumor samples used to establish PD-L1 expression for eligibility must have been collected after the most recent systemic therapy.

Thus, the study will include 6 parallel evaluations of clinical activity of Nivolumab combination regimens (Figure 1) in patients without prior treatment with a checkpoint inhibitor.

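### Do the opposing two-week windows make the two prior-checkpoint-outcome strata overlap in a way that needs a change to the plan?

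*Protocol*

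**What the plan says.** Protocol 3.2 splits CIT-experienced enrolment in each arm into two strata. The first covers patients who benefited from the earlier checkpoint inhibitor and then progressed radiographically. Benefit means response or "stable disease for at least 12 weeks [-2 week window permitted for radiograph scheduling". The second, labelled as having no prior clinical benefit, covers "radiographic progression of disease ≤ 12 weeks after initiation of treatment [+2 week window permitted for radiograph scheduling".

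The Study Summary ("RECIST defined partial, complete response or stable disease for at least 12 weeks") and SAP 6.2 ("SD for at least 12 weeks [-2 week window permitted for radiograph scheduling") carry the same definitions and windows. Inclusion criterion 2a requires only that the most recent treatment included a checkpoint inhibitor, "with the result of progression of disease on or after treatment"; it sets no time limit.

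The stratum is used in two ways:

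- **Stage decisions (Protocol 3.2).** With 9 evaluable patients, at least 1 response continues a stratum to 17. At 17, "If at least 3 Objective Responses are observed in a treatment stratum, further investigation may be warranted".
- **Analysis.** SAP 8.5 analyses each combination of arm and prior-benefit stratum separately and overall, and SAP 11.1.6 presents efficacy by arm and stratum.

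Beyond Stage 2, the sitravatinib CIT-experienced expansion "will be managed as one cohort that includes all patients, regardless of prior clinical benefit during treatment with CIT", up to 125 patients.

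**The concern.** Strata should be mutually exclusive and cover everyone eligible. Here the two limits share a 12-week cut, but the scheduling tolerance is subtracted from one and added to the other. The benefit stratum then accepts stable disease from 10 weeks, and the no-benefit stratum accepts progression up to week 14. A patient in between can satisfy both.

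Two further points are open. The wording does not settle whether the 12-week duration also limits complete and partial responses, or only stable disease. Nor does it say whether prior stable disease is counted to the last stable scan or to the date of progression.

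In an open-label study, discretionary placement of borderline patients could blur the contrast that the strata exist to show. With 9 and then 17 patients per stratum, the decision margins are a single responder. Patients enrolled in the lead-in or the pooled expansion, where prior benefit did not govern entry, also need a stratum label for the SAP tables.

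**Working it through.** **1. The plan's own figures.** For the rule of at least 1 of 9 and then at least 3 of 17 (Protocol 3.2), with p0 = 0.05 and p1 = 0.30:

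- Early termination under the null = (1 − 0.05)^9 = 0.6302 (stated 0.63).
- Probability of success = Σ over x = 1 to 9 of Bin(x; 9, p) × P[Bin(8, p) ≥ 3 − x]. This gives 0.0466 at p = 0.05 and 0.9045 at p = 0.30, both as stated.

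These depend on the number of patients and the response rate in a stratum, not on how its boundary is worded.

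**2. The overlap as written.** The benefit limit is 12 − 2 = 10 weeks and the no-benefit limit is 12 + 2 = 14 weeks. Stable disease at a scan in week 10 and progression in week 13 meets both.

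**3. When it could occur.** The documents give no prior-therapy scan schedule, so assume exact scans every k weeks, for k = 3, 4, 6, 7, 8, 9, 10 and 12.

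| Reading | Meets both | Meets neither |
|---|---|---|
| SD counted to last stable scan | none | k = 8 (SD 8, PD 16); k = 9 (SD 9, PD 18) |
| SD counted to PD date | k = 3 (SD 9, PD 12); k = 4 (8, 12); k = 6 (6, 12); k = 7 (7, 14) | none |
| Early CR/PR, confirmed at least 4 weeks later, then PD by week 14 | k = 3 (PR 3, confirmed 9, PD 12); k = 4 (4, 8, 12) | not applicable |
| Early CR/PR, unconfirmed responses counted | k = 3, 4, 6, 7 | not applicable |

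The first row matches the natural purpose of a scheduling window: a nominal 12-week scan may fall anywhere in weeks 10 to 14 and returns one result, stable or progressed. Overlap then needs two scans inside four weeks. Among exact schedules it first appears at k = 2 (SD 10, PD 12; SD 12, PD 14).

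The second row would credit 12 weeks of stable disease to a patient whose week-12 scan shows progression. Protocol Appendix 4 ties stable disease to a scan ("SD requires an on-study assessment after at least 6weeks on treatment") and requires CR and PR to be confirmed at least 4 weeks later. Neither rule is expressly extended to prior therapy, but nothing in the documents supports counting to the progression date.

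**4. What the labels settle.** The second stratum is defined by name as lacking prior benefit, and SAP 8.5 lists exactly two levels of the factor. A patient who meets the benefit definition cannot carry the other label. This resolves every case in the column of patients who meet both, including early responders.

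**5. Size of one misplacement.** As an illustration, move one responder, numerator and denominator together (Clopper-Pearson 95% CI):

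- 3/17 = 17.6% (3.8 to 43.4) becomes 2/16 = 12.5% (1.6 to 38.3), a change of −5.1 points.
- 2/17 = 11.8% (1.5 to 36.4) becomes 3/18 = 16.7% (3.6 to 41.4), a change of +4.9 points.

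**6. Reach.** SAP 4.1.1 limits glesatinib reporting to the lead-in, and SAP 4.1.2 records that mocetinostat never opened. Two strata remain, both sitravatinib. They share p0 = 5% and p1 = 30%, and SAP 11.1.6.1 tests CIT-experienced patients against 5%.

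**The case for a change.** The strongest case for a change is that the precedence is inferred, not written. One sentence would settle it, and the SAP describes itself as a living document with a final version due before database lock. The strata are still in use, because all efficacy analyses are split by them. The labels do not answer how stable-disease duration is counted, and they do not by themselves place the 8- or 9-weekly patient who meets neither definition. Irregular scans, which the windows anticipate, could produce overlap even under the last-stable-scan reading. In the illustration, the reassigned responder also crosses the line of 3 responses.

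The textual point stands: the windows do face each other, and the supplied documents hold no tie-break. A rule may exist in the Study Manual, which governs registration under Protocol 4.4 and was not available. The rest carries less weight. A two-level factor forces a placement, and a patient who progressed after week 14 has already failed the no-benefit definition. The 3-response line permits further investigation without mandating it, the stopping rules are recalculated for the actual evaluable number, and the protocol has already moved to a pooled expansion. Choosing a new cut-off now, in an open-label study whose preliminary activity results prompted that expansion, would be post hoc. A second set of stratum tables would add a data-informed comparison.

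**Conclusion.** The wording is loose, but no change to the plan follows. This is a gap that study staff and analysts can fill sensibly: benefit takes precedence, and the enrolment stratum is kept. The definitions overlap literally between 10 and 14 weeks. Read as tolerance around a single 12-week scan, they give no stable-disease overlap at the exact 3- to 12-weekly intervals checked; the remaining early-response cases are resolved by the stratum names.

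The possible effect is confined to stratum-level efficacy displays for the two sitravatinib CIT-experienced strata, at about 5 percentage points of ORR for each responder moved in a stratum of 17. Pooled ORR, the expansion to 125, type 1 error and power do not change.

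This rests on three assumptions: prior scans ran at roughly regular intervals, stable disease is counted to a scan, and the stratum names are followed. The number of borderline patients is unknown, so no gain from rewriting the definitions can be shown.
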